## 15.2 Short Form (36) Health Survey (SF-36)

The SF-36 is a multi-purpose, short-form health survey with 36 questions yielding 8 health domain scales and 2 psychometrically based physical and mental component summary measures. The standard form of the SF-36 Version 1 will be used and the raw data (questions), the scoring of health domains and the summary scores will be provided in SAS Format to Biostats by Data Management. The calculation of the derived scores will be done by validated CCI System.

The 8 health domain scales are referred to as the ‘Physical Functioning (PF)’, ‘Role- Physical (RP)’, ‘Bodily Pain (BP)’, ‘General Health (GH)’, ‘Vitality (VT)’, ‘Social Functioning (SF)’, ‘Role-Emotional (RE)’, and ‘Mental Health (MH)’ scales. The two summary measures are referred to as the physical component score (PCS) and mental component score (MCS).

For the scales and summary scores of the SF-36, the numeric values and corresponding changes from baseline will be summarized using descriptive statistics by parameter and time point.

The analysis will be carried out using a mixed model for repeated measures (MMRM), using all available measurements of the outcome of interest. The dependent variables will be the absolute change from baseline of the outcome of interest at the visits scheduled for Weeks 2 through 12, using fixed effects for treatment, visit, and the treatment x visit interaction and the baseline value as a fixed effect covariate. Treatment group comparisons in the change versus baseline at each visit will be estimated by differences between the marginal (adjusted) means from the treatment x visit interaction, with accompanying p-values and 95% confidence intervals.

Descriptive summary measures will be provided based on all observed values as well as based on the marginal means determined via MMRM analyses.

## 15.3 Corticosteroids and immunosuppressive drugs

Corticosteroid medications and immunosuppressive therapy will be identified through an ongoing medical review of the concomitant medications collected in the study, using an ad-hoc excel spreadsheet, including column “Immunosuppressant Yes/No” to flag corticosteroid medications

 CCI

CCI

and immunosuppressive therapy. The process will be performed before database lock. This excel spreadsheet (approved by the sponsor and provided together with the database extract by data management) will be imported via SAS and included in SDTM datasets by the statistical programmer.

Summary with counts and frequencies of patients with corticosteroid medications and immunosuppressive therapy presented at Baseline will be presented for Safety Analysis Set per study arm and overall.

In addition, counts and frequencies of these patients will be presented for an increased, decreased or a stopped dose. This summary statistic will be repeated for patients started a new therapy after Baseline. An increase (or decrease) of a dose is defined as a change in the average daily dose. Increase (or decrease) of dosing will be discussed and confirmed during the BDRM with the physician.

A by-patient listing will present all different medications and doses per visit.

## 16 SAFETY DATA

### 16.1 General considerations

Except for the analysis of extent of exposure and COVID-19 related AEs, analysis of safety has already been covered in Sections 13 and 14 above.

### 16.2 Extent of exposure

Exposure to the IMP (L-CsA or placebo) will be confirmed based on the difference between the number of IMP vials/ampoules dispensed and the number of unused vials/ampoules returned, and dosing recorded in the eCRF (this implies that IMP vials/ampoules not returned will be considered as having been used). Summary tables will be prepared including the following details about administration of L-CsA or placebo:

- Descriptive statistics for the total number of doses received.
- Descriptive statistics for the duration of treatment in days. For each patient, the treatment duration will be calculated as the difference between the dates of last and first administration of L-CsA (or placebo) plus 1.
- Descriptive statistics for the number of exposure days. For each patient, the number of exposure days is the count of unique days on which the patient received at least one administration of L-CsA (or placebo).

A by-patient listing will present all IMP administration data. This listing will include at least: date and time of L-CsA (or placebo) administration and L-CsA (or placebo) dose changed (yes, no, not applicable). If L-CsA (or placebo) dose changed, dose adjustment date and time and the reason for deviation will be displayed as well.

---

Moreover, a table of treatment compliance will be produced for the investigational treatment based on the ratio between the amount of IMP actually administered and the prescribed amount across the period between baseline and EoT. Treatment compliance will be categorized as <50%, 50-79%, 80-120% as well as >120%. Besides using the safety analysis set, this table will also be produced using the Full Analysis Set and the Per Protocol set.

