	
potential. A physical exam, including vital signs, will be performed. The CGI Questionnaire will be administered. The SF-36 Quality of Life Questionnaire will be administered. A dose of the IMP will be administered under observation. Patients will bring used and unused vials of the IMP for availability check.
 
Visit 3, Week 4: During on-site visits, spirometry will be obtained. Blood will be drawn for safety profiles and trough levels of CsA. A pregnancy test will be performed for all females of childbearing potential. A physical exam, including vital signs, will be performed. The CGI Questionnaire will be administered. The SF-36 Quality of Life Questionnaire will be administered. An Investigator's Tolerability Assessment will be performed. A dose of the IMP will be administered under observation during on-site visits. Patients will bring used and unused vials of the IMP for availability check at on-site visits.
 
Visit 4, Week 8: During on-site visits, spirometry will be obtained. Blood will be drawn for CsA trough level and safety parameters. A pregnancy test will be performed for all females of childbearing potential. A physical exam, including vital signs, will be performed. The CGI Questionnaire will be administered. The SF-36 Quality of Life Questionnaire will be administered. A dose of the IMP will be administered under observation during on-site visits. Patients will bring used and unused vials of the IMP for availability check at on-site visits.
 
Visit 5, Week 12 (EoT): Spirometry will be obtained. Blood will be drawn for CsA trough level and safety parameters. A pregnancy test will be performed for all females of childbearing potential. A physical exam, including vital signs, will be performed. The CGI Questionnaire will be administered. The SF-36 Quality of Life Questionnaire will be administered. An Investigator's tolerability assessment will be performed. Patients will return all used and unused vials of the IMP. Drug accountability will be performed. The L-CsA CCI will be returned.

--	---

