8.4 Investigational Medicinal Product Packaging, Labeling and Storage

8.4.1 Packaging and Labeling of IMP

Packaging

The IMP will be provided as 0 mg and 10 mg L-CsA lyophilisate in glass vials type I with grey rubber stoppers and an aluminum cap with a yellow plastic disk and stored in an outer packaging box consisting of 60 vials with the L-CsA/placebo and 70 plastic ampoules containing 2.4 mL 0.25% NaCl for reconstitution. The 5 mg L-CsA lyophilisate will be supplied in glass vials type I with grey rubber stoppers and an aluminum cap with a green plastic disk and stored in an outer packaging box consisting of 60 vials with the L-CsA and 70 plastic ampoules containing 1.2 mL 0.25% NaCl for reconstitution.

The IMP will be labelled in compliance with Good Manufacturing Practice (GMP) specifications according to applicable regulations.

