8.6 Investigational Medicinal Product: Supply and Accountability

Each Investigator is responsible for ensuring that deliveries of IMP vials and boxes, L-CsA CCI and other clinical trial materials are correctly received and recorded, that these are handled and stored safely in a locked and temperature controlled storage place with access for authorised study staff only and that they are used in accordance with this protocol. In addition, the Investigator will monitor each patient's treatment compliance by counting the used/unused drug vials at each visit.

For the purpose of this trial patients will be regarded as compliant if no more than 45 vials of IMP over the entire treatment period of 12 weeks are returned as unused – this corresponds to approximately 75% treatment compliance. The reason for non-compliance shall be documented according on the respective eCRF.

Unused IMP vials, ampoules, boxes, and L-CsA CCI must be returned or destroyed on-site after accountability has been completed and destruction is approved by Zambon SpA. A list of IMP, L-CsA CCI, and other materials received, used, returned, or destroyed must be prepared, completed and signed by the Investigator; any discrepancies must be accounted for.

COVID-19 specific consideration: the patients will be supplied during V1 with the full amount of study medication needed, to cover the total treatment period of 12 weeks. Patient has to bring all study medication back to the site at EoT Visit V5 for Drug Accountability.

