13.2.3 Visit 2 through Visit 5 / EoT

- Physical examination
- Vital signs
- Clinical laboratory tests
- Cyclosporine A whole blood trough levels (blood sample pre-dose)
- Urine/Serum pregnancy test
- Spirometry
- IMP Administration
- Concomitant medications/therapies
- AEs
- CGI (Items 1-3)
- SF-36 questionnaire
- Local IMP tolerability
- Drug Accountability by vial count (Visit 5 only)
- Check IMP supplies of patient

13.2.4 Visit 3 and Visit 5

- In addition to the assessments described in section 13.2.3, the clinical investigator will perform an Investigator's Tolerability Assessment assessed by means of a five-point verbal rating scale with the response options 'very good', 'good', 'satisfactory', 'moderate', and 'poor'.

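### SAP 16.2 counts unreturned drug as used, so vial-based total doses and compliance show a full course for a patient who stops early and returns nothing

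*SAP*

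**What the plan says.** SAP 16.2 takes exposure from items dispensed minus unused items returned, "and dosing recorded in the eCRF". It then spells out the consequence for missing items: "this implies that IMP vials/ampoules not returned will be considered as having been used". It does not say which source prevails if the two disagree. Treatment duration and exposure days are defined from administration dates. Compliance is the ratio of drug administered to drug prescribed between baseline and end of treatment (EoT), in the categories <50%, 50–79%, 80–120% and >120%.

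On supply, Protocol 8.6 says "the patients will be supplied during V1 with the full amount of study medication needed, to cover the total treatment period of 12 weeks". Protocol 13.2.2 and SAP 8.1 agree. A box of the 10 mg or placebo product holds "60 vials with the L-CsA/placebo and 70 plastic ampoules" of diluent (Protocol 8.4.1), and the 5 mg box has the same counts.

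On returns, the synopsis entry for Visit 5 reads "Patients will return all used and unused vials of the IMP". For patients who leave early, Protocol 8.5.1 and 9.3.1 plan retrieval of used and unused drug only where applicable.

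On counting, Protocol 8.6 has the investigator "counting the used/unused drug vials at each visit", whereas Protocol 13.2.3 lists "Drug Accountability by vial count (Visit 5 only".

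**The concern.** Counting missing drug as taken does little harm when drug is issued in small lots, because the error cannot exceed one lot. Here the single lot is the whole course. A patient who is lost or withdraws without bringing drug back has no unused vials on record, so the subtraction returns the full supply whatever was inhaled.

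Two further points make the result unstable. The SAP wording lets vials or ampoules be counted, although the ampoules hold only diluent and outnumber the vials. The compliance ratio also has no stated denominator for a patient whose EoT comes early.

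At stake are the dose totals and the compliance table, which is produced for the SAF, FAS and PPS. Non-compliance is also among the deviations assessed under SAP 10.1, so a wrong count could reach that review. In a tolerability trial with 8 patients per arm, one wrong total visibly shifts an arm's mean.

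**Working it through.** **Inputs.** Two inhalations a day (Protocol 8.3.2.3) for 12 weeks; 60 vials and 70 ampoules per box (Protocol 8.4.1); 8 patients per arm (Protocol 14.5). The number of boxes issued is not stated. Three is the smallest number that covers the course and is assumed below.

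**Planned course.** 12 × 7 × 2 = 168 doses. Three boxes give 3 × 60 = 180 vials and 3 × 70 = 210 ampoules.

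**The plan's own figure.** Protocol 8.6 equates at most 45 vials returned unused with about 75% compliance. With 180 vials, (180 − 45)/180 = 75.0%. With exactly 168 vials, (168 − 45)/168 = 73.2%. Both fit, and the three-box assumption fits exactly. A patient who returns nothing has zero unused vials on record and so meets this limit too.

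**SAP rule for a patient who stops early and returns nothing.** Recorded doses = dispensed − 0 = 168 to 180. Full adherence up to the stop gives the most that could have been taken. The stop weeks are illustrative.

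| Stops after week | Most doses taken | Share of 168 | True category | Recorded, over 168 | Recorded, over doses due by the stop |
|---|---|---|---|---|---|
| 2 | 28 | 16.7% | <50% | 100–107% (80–120%) | 600–643% (>120%) |
| 4 | 56 | 33.3% | <50% | 100–107% (80–120%) | 300–321% (>120%) |
| 8 | 112 | 66.7% | 50–79% | 100–107% (80–120%) | 150–161% (>120%) |

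The last two columns differ only in the denominator, which SAP 16.2 leaves open for early stoppers.

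**Ampoules counted instead of vials.** 210/168 = 125%, category >120%. This would apply even to a patient who took all 168 doses but did not return the spare diluent.

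**Effect on an arm of 8, the others at 168.** With one week-2 non-returner, the true mean is (7 × 168 + 28)/8 = 150.5. The recorded mean is 168 (168 vials) or (7 × 168 + 180)/8 = 169.5. The excess is 17.5 to 19 doses, or 10.4% to 11.3% of 168. With two, the true mean is (6 × 168 + 2 × 28)/8 = 133 and the recorded mean is 168 to 171.

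**The case against.** The strongest reply is that the vial difference is not the only source. SAP 16.2 and Protocol 14.2.3.1 also name eCRF dosing, and the SAP's line on total doses gives no formula. That stands, and it means the full-course result belongs to the vial-based figures and is not certain for every output. It does not remove the problem. The SAP gives no precedence, it states outright what happens to unreturned items, and neither document describes a diary through which home doses would reach the eCRF.

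Second, other outputs would reveal an early stop. Duration and exposure days are date-based, discontinuation is recorded with date and reason (Protocol 9.3.2), and events leading to treatment discontinuation are tabulated (SAP 13.3.1). This stands where the last dose date is known.

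Third, patients who stop drug are asked to keep attending (Protocol 9.3.1), and Visit 5, where drug is handed back, is mandatory on site. Those who return their unused drug are counted correctly. This also stands.

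Fourth, a value far above 120% would itself look anomalous. That is true of the short-denominator and ampoule cases, but not of the 80–120% case, where nothing signals an error.

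A reader might go further and infer that a poorly tolerated dose would look well tolerated in the primary results. The documents do not support this. The primary outputs are proportions of patients with events and incidence densities per patient day, no safety analysis by doses received is planned, and nothing links failure to return drug with intolerance.

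A reader might also infer that dosing in the first 4 weeks is never measured. That is too strong. The eCRF record and the listing of administration dates and times cover the window, and vials are brought to Visit 2 and to on-site Visits 3 and 4 for an availability check. Under Protocol 13.2.3, only a formal vial count is missing until Visit 5.

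**Conclusion.** The point holds for two outputs: vial-based total doses and the compliance ratio. For an early stopper who returns nothing, the stated rule yields 168 doses, or 180 under the three-box assumption, however few were taken. At week 2 the most that could have been taken is 28, so the overcount is at least 6.0-fold (168/28), or 6.4-fold with 180 vials. The patient moves from <50% to 80–120%, or to >120% depending on the denominator and the item counted.

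The size for the trial as a whole cannot be stated, because the documents give no expected number of non-returners. The arm-level figures assume one or two such patients, both stopping at week 2, with all others taking every dose. The error does not reach the date-based exposure measures when the last dose date is known, patients who return their drug, or any primary event analysis. It should be corrected because the rule is explicit, its result is wrong in a foreseeable case, and the remedy is cheap.

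**What to change.** In SAP 16.2:

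- Count drug vials only, not ampoules.
- Replace the rule that unreturned means used with a category for vials unaccounted for. Cap doses received at two per day from the first to the last administration documented in the eCRF.
- Where vials are unaccounted for, show a range. The lower bound is documented administrations plus returned used vials, without double counting. The upper bound is the capped figure. Returned used vials alone would not serve as the lower bound: they give zero for a non-returner whose first dose was supervised at Visit 1.
- State which source prevails when the vial count and the eCRF disagree, and define the compliance denominator for patients who stop early.

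For the week-2 example the upper bound becomes 28 instead of 168 to 180, provided the last dose date is documented.

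In the protocol, reconcile 8.6 with 13.2.3 so that vials already brought to on-site Visits 2 to 4 are counted there. Doses received up to Visit 3 can then be reported beside the primary tables. Protocol 8.4.3 still mentions a monthly supply at later clinic visits and should be reconciled with full supply at Visit 1.

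The cost is SAP wording, light programming and brief counting at on-site visits. Exposure for some patients will appear as a range that looks less favourable than a single figure.

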### **16.3 COVID-19 specific considerations**

COVID-19 related AEs using COVID-19 (SMQ) available at <https://www.meddra.org/COVID-19-terms-and-MedDRA> will be reported as SAEs. All confirmed cases of COVID-19, occurring after the patient has provided informed consent will be summarized in a table and flagged in the AE subject data listing.

The seriousness criterion for COVID-19 hospitalized patients should be “hospitalization”; if the patient was not admitted to a hospital or the event is not resulting in prolonged hospitalization, the seriousness criterion “medically significant” will be used.

In all cases, details of the patient's symptoms, treatment and any clinically relevant information, from the SAE CRF-form will be presented in a separate subject data listing.

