	
Visit 6, Week 14 (EoS): Blood will be drawn for safety parameters. A pregnancy test will be performed for all females of childbearing potential. A physical exam, including vital signs, will be performed.
 
Safety and tolerability will be monitored by documentation of AEs throughout the study.
 
Every effort will be made to have all planned and unscheduled visits at the study site. Mandatory on site visits are Screening and Visit 1, Visit 2 and Visit 5.
 
However, if one of the visits V3, V4 and V6 cannot be performed at site due to COVID-19, remote visits (e.g. by telephone) are possible. COVID-19 related Adverse Events will be reported as SAEs.

Data Monitoring Committee:	
A Data Monitoring Committee (DMC) is established to monitor the safety of IMP. The DMC will monitor safety by evaluating the safety analyses generated by the independent statistician during the course of the clinical trial. Details of the safety analyses will be included in the DMC Charter.
 
The DMC will evaluate treatment groups for possible trends in AEs, determine whether the basic protocol assumptions remain valid, evaluate whether the overall integrity, scientific merit and conduct of the clinical trial remain acceptable, and make recommendations to the Sponsor.

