In addition to the Investigator's own description of the AE, each AE event will be coded by data management according to the Medical Dictionary for Regulatory Activities (MedDRA) code list. The verbatim term will be recorded in the eCRF.

Abnormal laboratory test results will be reported as AEs if they are indicative of a clinical condition that meets the criteria for an AE.

Adverse Drug Reaction (ADR)

Adverse drug reactions (ADRs) are all noxious and unintended responses to a medicinal product related to any dose that a causal relationship between the medicinal product and an AE is at least a reasonable possibility, i.e., the relationship cannot be ruled out. An unexpected ADR is any adverse reaction not identified in nature, frequency, or intensity listed in the referent safety section of the current IB.

Serious Adverse Event (SAE)

Each AE is to be classified by the Investigator as SERIOUS or NON-SERIOUS.

The International Conference on Harmonisation (ICH) of Technical Requirements for Registration of Pharmaceuticals for Human Use defines an SAE as any AE occurring at any dose that results in any of the following outcomes:

- Death
- A life-threatening event (immediate risk of death at the time of the event)
- Inpatient hospitalization or prolongation of existing hospitalization
- A persistent or significant disability/incapacity
- A congenital anomaly/birth defect
- Other important medical event (Medical and scientific judgment should be exercised in deciding whether expedited reporting is appropriate in other situations, such as important medical events that may not be immediately life-threatening or result in death or hospitalization but may jeopardize the patient or may require intervention to prevent one of the other outcomes listed in the definition above. These should also usually be considered serious.)

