12.1.4.2 Other Events to be treated as Serious Adverse Events

Exposure to drug during pregnancy/lactation:

In principle, pregnancy and the lactation period are exclusion criteria. In the event of a pregnancy occurring during the course of the clinical trial, the patient must be withdrawn from all IMP treatment immediately and permanently. The Sponsor must be notified without delay by completing the Pregnancy Form A and the patient followed during the entire course of the pregnancy and postpartum period. Prenatal and neonatal outcomes must be recorded even if they are completely normal and without AEs. The pregnancy reporting timelines are the same as described for SAE reporting procedure in [section 12.1.4](#).

If any clinical trial patient becomes pregnant during the clinical trial period, the Investigator must contact Zambon SpA as the Sponsor of the clinical trial or its designee to discuss the management of the patient.

Adverse Device Effect

In principle, serious adverse events caused by a device issue should be reported as SAEs as described above.

Other device deficiencies and malfunctions not associated with the adverse event should be reported via the **CCI** Complaint Form, provided in the IMP manual.

COVID-19 specific considerations:

All confirmed cases of COVID-19, occurring after the patient has provided informed consent and until 4 weeks after the EoT visit, must be reported as SAE and reported to **CCI** within 24 hours upon knowledge.

The seriousness criterion for COVID-19 hospitalized patients should be “hospitalization”; if the patient was not admitted to a hospital or the event is not resulting in prolonged hospitalization, the seriousness criterion “medically significant” should be used.

In all cases, details of the patient's symptoms, treatment and any clinically relevant information, should be entered in the SAE forms, as appropriate.

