## **13.3 Analysis of Safety**

### **13.3.1 Adverse events (non-serious or serious)**

AEs will be coded using the MedDRA. The version of the utilized dictionary will be presented either in the title or footnote of the provided tables and by-patient listings. Events will be identified as treatment-emergent (TEAE) and non-treatment-emergent (Non-TEAE) on the basis of the date of onset relative to the date of the first IMP dose. Events with an onset date before the date of the first IMP dose will be defined as Non-TEAE. Events with an onset date on or after the first IMP dose or pre-existing and worsening after IMP intake will be defined as TEAE.

---

For all TEAEs occurring during the first 4 weeks of treatment (on or before Visit 3), and separately for all TEAEs (i.e. events with onset at any time during randomized treatment, as secondary assessment, please refer to section 8.4), a summary containing the following counts and percentages of subjects will be presented by treatment group and overall:

- Overview table, including the number (percent) of patients with
  - Any TEAEs
  - Mild TEAEs
  - Moderate TEAE
  - Severe TEAEs,
  - Serious TEAEs
  - Treatment-related TEAEs,
  - Serious Treatment-related TEAEs,
  - COVID-19 related TEAEs;
  - TEAEs leading to discontinuation of study,
  - TEAEs leading to discontinuation of treatment,
  - TEAEs having an outcome of death.

AEs leading to discontinuation of study are identified as AEs whose CRF field in AE form “Study discontinued due to this (S)AE” is flagged as “Yes”.

AEs leading to discontinuation of treatment are identified as AEs whose CRF field in AE form “Action taken” is flagged as “Treatment stopped”.

Patients who have multiple events will be counted only once but all events will be considered as occurred.

Summaries (number of events as well as number and percentage of patients with any events of a particular type) of TEAEs will be provided by primary system organ class (SOC) and preferred term (PT) and will be ordered in terms of decreasing frequency for SOC, and PT within SOC, in the total column. Patients who have multiple events coding to the same PT or within the same SOC will be counted only once in the patient counts for the corresponding summaries, but all events will be considered and listed. Patients who experience the same event multiple times will be included in the most severe category where applicable.

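### The documents disagree on which COVID-19 events count as SAEs, and no planned table shows the primary serious-TEAE counts without them

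*SAP*

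**What the plan says.** Four places state the rule.

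- Protocol 12.1.4.2: "All confirmed cases of COVID-19, occurring after the patient has provided informed consent and until 4 weeks after the EoT visit, must be reported" as SAEs.
- Protocol synopsis, Assessments: "COVID-19 related Adverse Events will be reported as SAEs", with no restriction to confirmed cases. SAP 8.1 repeats this sentence.
- SAP 16.3, first sentence: "COVID-19 related AEs using COVID-19 (SMQ) available at" a MedDRA web page are to be reported as SAEs. The scope of the search (narrow or broad) is not stated.
- SAP 16.3, second sentence: "All confirmed cases of COVID-19, occurring after the patient has provided informed consent will be summarized in a table and flagged" in the AE listing. Confirmed cases are thus handled separately from the SMQ set.

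Protocol 12.1.4.2 and SAP 16.3 assign the seriousness criterion in the same way. It is hospitalization for hospitalized patients; "if the patient was not admitted to a hospital or the event is not resulting in prolonged hospitalization, the seriousness criterion" is medical significance.

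Protocol 12.1.1 has the investigator classify each AE as serious or not. One of its listed criteria is "Other important medical event (Medical and scientific judgment should be exercised in deciding whether expedited reporting is appropriate in other situations".

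SAP 8.3 places SAEs among the primary endpoints. The overview table in SAP 13.3.1 has a row for serious TEAEs and another for "COVID-19 related TEAEs", for events up to Visit 3 and again for the whole treatment period. The same section plans COVID-19 TEAE tables and serious TEAEs by seriousness criterion.

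**The concern.** A count of serious events is normally read as the investigators' judgment of how grave the events were. If a dictionary search decides part of it, the count also reflects who caught COVID-19, and how broadly the search was set. In a 24-patient trial run during the pandemic, a difference of one or two patients between arms could come from that source alone.

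SAP 6 says the SAP governs the analysis where it conflicts with the protocol. Its table of differences has no entry for the SMQ, which appears only in the SAP. A programmer following SAP 16.3 word for word would therefore have authority to count SMQ hits as serious. A reader of the report would have no summary of serious TEAEs without them.

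**Working it through.** No planned figure depends on this rule, so there is none to reproduce. The check is a comparison of the texts, followed by arithmetic for scale.

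**Texts side by side**

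| Place | Events covered | End of window |
|---|---|---|
| Protocol synopsis | COVID-19 related AEs | not given |
| Protocol 12.1.4.2 | confirmed cases | 4 weeks after EoT |
| SAP 8.1 | COVID-19 related AEs | not given |
| SAP 16.3, SAE rule | COVID-19 related AEs found by SMQ | not given |
| SAP 16.3, table and flag | confirmed cases | not given |

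Three things follow.

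1. The protocol differs from itself (synopsis against 12.1.4.2). The SAP follows the wider wording and adds a search definition.
2. SAP 16.3 does not fit together for an unconfirmed hit. It takes the details of all cases from the SAE form, but an event that the investigator did not report as an SAE has no such form. The programmer must then override the eCRF or disregard the sentence.
3. The window also differs. Protocol 12.1.4 and 12.1.4.5 follow SAEs to 2 weeks after EoT, whereas 12.1.4.2 runs to 4 weeks.

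**Can the planned tables be subtracted?** Suppose an arm has 2 patients in the serious row and 1 in the COVID-19 row, that patient's COVID-19 event being counted as serious. If this patient had no other serious event, 1 of 8 (12.5%) had a serious event other than COVID-19. If the patient had one, it is 2 of 8 (25%). The two rows do not say which. The table by seriousness criterion does not settle it either, because other events can also be medically significant.

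**Scale.** Inputs: n = 8 per arm (SAP 9.2), two-sided 95% intervals (SAP 9.1), Wilson score method (SAP 13.3.1). With p = x/n and z = 1.96, the limits are

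[p + z²/(2n) ± z·√(p(1−p)/n + z²/(4n²))] / (1 + z²/n).

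For n = 8, z²/(2n) = 0.240 and 1 + z²/n = 1.480.

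- 0/8: 0 to 2 × 0.240/1.480 = 32.4%.
- 1/8: (0.125 + 0.240)/1.480 = 0.247; half-width 1.96 × √(0.01367 + 0.01501)/1.480 = 0.224; limits 2.2 to 47.1%.
- 2/8: (0.25 + 0.240)/1.480 = 0.331; half-width 1.96 × √(0.02344 + 0.01501)/1.480 = 0.260; limits 7.1 to 59.1%.

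Each added patient moves the proportion by 1/8 = 12.5 points. The SAP does not name a method for the difference. With Newcombe's method, built from the Wilson limits, 1/8 against 0/8 gives 12.5 points (−21.5 to 47.1), and 2/8 against 0/8 gives 25 points (−12.0 to 59.1).

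**How many events?** The documents do not say. As an assumption only, if 5% to 30% of patients had an unconfirmed SMQ hit in the window considered, that is 24 × 0.05 = 1.2 to 24 × 0.30 = 7.2 patients. The chance of at least one in an arm of 8 is 1 − 0.95⁸ = 34% to 1 − 0.70⁸ = 94%.

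**The case against.** The case against is substantial, and much of it stands.

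- A reader might infer that the serious counts will hold events meeting no seriousness criterion. The text does not support this. Both documents assign medical significance to COVID-19 without hospitalization, and an important medical event is a listed criterion in protocol 12.1.1. What remains is that the criterion is assigned by rule and not case by case.
- A reader might infer that the SAP departs from the protocol. It departs from protocol 12.1.4.2 but agrees with the synopsis.
- A reader might infer that the SAP overwrites the investigator's seriousness flag. No such step is described. The sentence may only restate the reporting duty, and the reference to the SAE form suggests events already entered as SAEs. The wording still allows either reading.
- The scale figures apply equally to a mild confirmed case, which protocol 12.1.4.2 already makes an SAE. The SAP's own excess is limited to unconfirmed hits, whose number is unknown. The Wilson comparisons are also planned for TEAEs, pairwise by SOC, and not expressly for the serious row.
- Much is visible already: a COVID-19 row, COVID-19 tables, a flag in the AE listing and a separate listing. With 24 patients, a reader could rebuild most of the count by hand. However, the listing flag is tied to confirmed cases, so unconfirmed SMQ hits may go unmarked.
- The analysis is descriptive, with no hypothesis and no stated decision threshold on the SAE count. This limits the consequence, but the count is still part of the primary assessment.

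**Conclusion.** The concern holds in a limited form. The four statements contradict each other on confirmed cases versus COVID-19 related AEs. Followed literally, SAP 16.3 would put events into the primary serious-TEAE rows by term search, and no planned summary shows those rows without COVID-19 events.

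The effect is 12.5 points per patient in an arm of 8. Its total cannot be given, because neither the number of events nor the content of the SMQ is in the documents. The conclusion assumes that the SAP sentence is applied as written. If it only restates the reporting duty, what remains is unclear wording and a missing row. The severity is minor.

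**What to change.** 1. Reconcile the protocol synopsis, protocol 12.1.4.2, SAP 8.1 and SAP 16.3 on confirmed cases versus COVID-19 related AEs, and on the end of the window. If a difference from the protocol remains, enter it in the table in SAP 6.
2. In SAP 16.3, state the SMQ scope, use the SMQ only to identify and flag events, and take seriousness from the eCRF.
3. In SAP 13.3.1, add to the overview and the serious-TEAE tables one row for serious TEAEs excluding COVID-19 events, beside the all-serious row. State which COVID-19 definition the row uses.

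Restricting the serious rows to the ICH criteria would not do the same job, because medical significance is one of those criteria and the events would stay in. An excluding row needs only the COVID-19 flag, with no new data item or case review.

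Safety reporting duties and data collection stay as they are. The cost is SAP wording, alignment of the protocol text, and one row per table.
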